Study TH-CR-602 enrolled 30 patients. In combining the results of both studies, the most common AE was ECG QT prolongation, which occurred in 35/51 (68.6%) of the patients and in these 35 patients, 19 (54.3%) were Grade 3 severity and 16 (45.7%) less than Grade 3. Skin and subcutaneous tissue disorders were experienced by patients and the most frequent were dermatitis acneiform 13/51 (25.5%), rash 7/51 (13.7%), and pruritus 5/51 (9.8%) and most were \leq Grade 2 in severity. The other most common treatment-related AEs were diarrhea (35.3%, 18/51) and fatigue (17/51, 33.3%).

Special emphasis was placed on QT monitoring in both studies. This included Holter monitoring during Cycle 1 Day 1 and calibrated ECG machines with central reading of ECG measurements throughout the study duration. Holter monitoring was used to record and extract triplicate QT measurements at 9 predefined time points during the first 24 hours of Cycle 1 Day 1 in both studies. The mean maximum QTcF change from baseline was 51 msec occurring 3 hours after the end of infusion and 55 msec occurring 2 hours after the end of infusion in Study TH-CR-601 and Study TH-CR-602, respectively. Across the 2 studies, 10 patients (21%) developed QTcF values \geq 501 msec and 16 patients (34%) developed a QTcF change from baseline of > 60 msec. The time-matched PK and QTcF data suggest a QT prolongation hysteresis of up to 2 to 3 hours after the tarloxotinib C_{max} which occurs at the end of infusion. T-wave segmentation analysis suggests that tarloxotinib is a hERG channel blocker and that it does not possess mitigating multichannel blocking properties.

Please refer to the Tarloxotinib Investigator's Brochure for the most current safety assessment.

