2.5 Rationale for Dose Selection and QT Prolongation Mitigation

This study will evaluate tarloxotinib 150 mg/m² as a weekly 1-hour IV infusion (the MTD declared in the first-in-human Phase 1 study (Patterson 2013) and the dose level explored in the 2 Phase 2 studies). Preclinical xenograft studies utilizing weekly doses of tarloxotinib at human equivalent of the clinically assessed dose (48 mg/kg intraperitoneally weekly equivalent to 150 mg/m² IV weekly) induced marked tumor shrinkage and marked inhibition of EGFR phosphorylation for 7 days suggesting protracted tumor residence time for tarloxotinib-E. Furthermore, this dose was associated with low-grade skin rash and diarrhea, suggesting limited systemic EGFR inhibition, indicating an on-target pharmacodynamic effect in man. It is expected that enhanced activation in the tumor compared to normal tissue may offer a therapeutic advantage over standard TKIs in terms of the potential for enhanced intra-tumoral blockade of EGFR signaling with acceptable tolerability.

Tarloxotinib was associated with Grade 1 or Grade 2 QTc prolongation starting at a dose of 40 mg/m² and more consistent QTc prolongation at 150 mg/m² suggesting a dose-dependent effect. However, extending the infusion duration from 1 hour to 24 hours, which reduced the tarloxotinib C_{max} approximately 6-fold, did not appear to have an impact on QTc prolongation at the 200 mg/m² dose of tarloxotinib in the 2 patients evaluated. Time-matched assessment of QTc changes from baseline with tarloxotinib plasma concentrations after a 150 mg/m² dose from the Phase 2 studies did not suggest an exposure correlation. What is evident, is that there was a time-delay of the maximum QTc prolongation from baseline from the time to maximum tarloxotinib exposure of about 3 hours (QT prolongation hysteresis). During this period, patients are at greatest risk of developing QT-related cardiac arrhythmias, such as Torsade de Pointes (TdP). The QT prolongation risk mitigation strategy includes several layers of precautions, as follows:

- Eligibility criteria that exclude patients at increased risk, such as:
 - o History of long QT syndrome, TdP, or family history of sudden death
 - o Receiving medication that prolongs QTc interval
 - Baseline QTcF \geq 450 msec
 - o Significant cardiovascular disease
- Repeated ECG measurements during the study (prior to and following the infusion)
- Potassium supplementation prior to dosing, as needed (Section 6.4)

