- All patients are under direct supervision of qualified personnel with immediate availability of appropriate resuscitation equipment. Patients will therefore be under intense monitoring and supervision during the entire period they are at risk for QT prolongation.
- Patients will not be discharged unless they have ≤ Grade 2 QTcF.

In the prior Phase 1 and 2 Phase 2 studies, the main identified risk of tarloxotinib treatment (QT prolongation) was observed primarily within a 3- to 4-hour period following the start of infusion.

Confidential and Proprietary

Given the absence of effective treatment options for NSCLC patients with EGFR exon 20 insertion or HER2-activating mutations and based upon the manageability of observed risks associated with tarloxotinib, the risk-to-benefit ratio for participants in this study is acceptable. This risk of QT prolongation is mitigated in this study by the medical supervision of patients during first 3 to 4 hours of drug administration, when the risk of an event is greatest, with additional guidance on management of QT prolongation provided in the protocol and the Tarloxotinib Investigator's Brochure.

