2.6 Potential Risks

Cancers harboring the mutations and fusions under evaluation in study RAIN-701 have been generally refractory to currently available therapies. Tarloxotinib is an investigational agent with no proven clinical benefits. As of the start of this clinical trial, tarloxotinib had been administered to 84 adults with a variety of cancer types. In the combined dataset of Studies TH-CR-601 and TH-CR-602 (n = 51), where tarloxotinib was administered as a 1-hour weekly IV infusion at a dose level of 150 mg/m², the most commonly reported AEs included ECG QT prolongation, diarrhea, fatigue, dermatitis, rash, pruritus, nausea, and cough. Infusion-related reactions characterized by flushing, urticarial skin rash, pruritus, and hypotension have been observed during and immediately following infusion of tarloxotinib. All patients receiving tarloxotinib should be instructed to seek immediate medical care in the event allergic symptoms develop.

Prolongation of the QT interval have been observed up to 4 hours following completion of tarloxotinib infusion. At the recommended dose of 150 mg/m², AEs of QT prolongation were reported by 35/51, 68.6% (19 of these patients experienced Grade 3 QTc prolongation). There was 1 patient who experienced a Grade 3/Grade 4 event at the 335 mg/m² dose level in the Phase 1 study). QT prolongation can infrequently lead to serious (rarely fatal) fast and irregular heart rhythms and other symptoms, such as severe dizziness and/or fainting, seizure, and palpitations. Patient eligibility criteria and monitoring have been implemented based on these past findings.

Due to the possibility of phototoxicity, patients should be instructed to avoid prolonged exposure to sunlight while on study treatment and when exposure cannot be avoided to use a broad-spectrum sunscreen.

Please refer to the most recent version of the Tarloxotinib Investigator's Brochure for the most current understanding and management of the potential risks associated with the use of tarloxotinib.

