6.7.1 Treatment Guidelines for QTc Prolongation

Immediate medical management of patients will be based on the following:

- 1. Baseline: A pre-infusion (baseline) ECG will be obtained on all patients, if the automated measurements indicate a QTcF of \geq 450 msec
 - a. The single QTcF will be verified by manually measuring at least 3 complexes within the ECG and determining the average QTcF
 - b. All patients must have a pre-infusion QTcF of < 450 msec by either:
 - i. Calculation using the automated measurements of the first ECG or
 - ii. The manual measurement of a single ECG

If it is determined that the manually read QTcF \geq 450 msec, the Medical Monitor should be contacted to discuss the clinical significance of the reading and to determine if it is appropriate to move forward with the infusion.

2. During treatment: Grade 3 QTc prolongation (any QTcF that is ≥ 501 msec OR > 60 msec QTcF increase relative to pre-infusion) will be manually verified by measuring at least 3 complexes with the ECG and determining the average QTcF. If QTcF prolongation is ≥ Grade 3, an ECG may need to be repeated more frequently during a patient's visit, depending on the degree of the prolongation, as indicated in Table 7 and per institutional standards.

Note: Dose modification will be based on the average QTcF using the manual measurements.

Confidential and Proprietary

If the Investigator has any question regarding the local automated reading, a local cardiologist should be consulted. Treatment guidelines for patients experiencing QTc prolongations are provided in (Table 7).

Patients who experience \geq Grade 3 QTc prolongation must be assessed by the Investigator (or qualified designee) prior to discharge.

Table 7: Treatment Guidelines for QTc Prolongation

QTc Prolongation	After Tarloxotinib Administration		
Grade 1 450 to 480 msec QTcF	 Cycle 1 and Cycle 2 Day 1 May be discharged if the 4-hour (or later) post-infusion QTcF is Grade 1 or lower and asymptomatic After Cycle 2 Day 1 Obtain pre-infusion and 2-hour post-infusion ECGs May be discharged if the 2-hour (or later) post-infusion QTcF is ≤ Grade 1 and the patient is asymptomatic 		

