Grade 2 481 to 500 msec QTcF	 Continue the same tarloxotinib dose for subsequent cycles Cycle 1 and Cycle 2 Day 1 May be discharged if the 4-hour (or later) post-infusion QTcF is ≤ Grade 2 and the patient is asymptomatic After Cycle 2 Day 1 Obtain pre-infusion and 2-hour post-infusions ECGs May be discharged if the 2-hour or later post-infusion QTcF is ≤ Grade 2 and the patient is asymptomatic Continue the same tarloxotinib dose for subsequent cycles 		
Grade 3 ≥ 501 msec QTcF	 Obtain ECGs every 15 to 30 minutes until QTcF is ≤ Grade 2 and then obtain ECGs every 1 hour May be discharged home if 2 subsequent measurements (at least 15 minutes apart) after the 4-hour post-infusion QTcF is ≤ Grade 2 and no significant arrhythmias If QTcF is ≥ 601 msec, permanently discontinue tarloxotinib If QTcF ≥ 501 msec and ≤ 600 msec Resume tarloxotinib dosing with dose reduction 1st occurrence: reduce to 100 mg/m² 2nd occurrence: reduce to 75 mg/m² 3rd occurrence: permanently discontinue tarloxotinib Obtain ECGs prior to and hourly (for at least 4 hours) following the next tarloxotinib infusion 		
Grade 3 > 60 msec increase from pre-infusion QTcF AND ≤ 500 msec QTcF	 Obtain ECGs every 15-30 minutes until QTcF is ≤ Grade 2 and then obtain ECGs every 1 hour May be discharged home if 2 subsequent measurements (at least 15 minutes apart) after the 4-hour post-infusion QTcF is ≤ Grade 2 and no significant arrhythmias Obtain ECGs prior to and hourly (for at least 4 hours) following the next tarloxotinib infusion 		
Grade 4 TdP or polymorphic ventricular tachycardia, signs/symptoms of serious arrhythmia	Place patient on telemetry and obtain ECGs as clinical indicated Obtain Cardiologist consult and admit to hospital for extended observation on telemetry Permanently discontinue tarloxotinib		

ECG = electrocardiogram; msec = millisecond; QTcF = corrected QT interval as calculated according to Fridericia's formula; TdP = Torsade de Pointes

Note: If QTcF prolongation is ≥ Grade 3, an ECG may need to be repeated more frequently during the patient's

Confidential and Proprietary

visit depending on the degree of the prolongation and per institutional standards.

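### After Cycle 2 Day 1 the protocol allows discharge on a 2-hour ECG, although its own data put one mean QTcF peak at 3 hours and prolongation up to 4 hours after infusion, and the SAP describes a different ECG schedule

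*Protocol*

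**What the plan says.** **Discharge.** In Cycle 1 and on Cycle 2 Day 1, the Grade 2 row of Protocol Table 7 (Section 6.7.1) reads "May be discharged if the 4-hour (or later) post-infusion QTcF is ≤ Grade 2 and the patient is asymptomatic". After Cycle 2 Day 1 it changes to "Obtain pre-infusion and 2-hour post-infusions ECGs" and "May be discharged if the 2-hour or later post-infusion QTcF is ≤ Grade 2 and the patient is asymptomatic". The Grade 1 row steps down in the same way: "May be discharged if the 2-hour (or later) post-infusion QTcF is ≤ Grade 1 and the patient is asymptomatic".

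**ECG schedule.** Section 6.9.2 gives every patient ECGs out to 4 hours in Cycle 1 and on Cycle 2 Day 1. After that the 2-hour ECG is for everyone. The 4-hour ECG is for patients with Grade 3 or higher prolongation (Days 8, 15 and 22 of Cycles 2+) or QTcF of 501 msec or more (Day 1 of Cycles 3+), with hourly ECGs as needed.

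**Risk period.** Section 2.3.2, from Holter recordings on Cycle 1 Day 1, states: "The mean maximum QTcF change from baseline was 51 msec occurring 3 hours after the end of infusion" in TH-CR-601; the figure for TH-CR-602 is 55 msec at 2 hours. Section 2.5 gives a lag of about 3 hours from peak exposure to peak QTc and says "During this period, patients are at greatest risk of developing QT-related cardiac arrhythmias". It then promises: "Patients will therefore be under intense monitoring and supervision during the entire period they are at risk for QT prolongation". Section 2.6 says: "Prolongation of the QT interval have been observed up to 4 hours following completion of tarloxotinib infusion".

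**SAP.** Section 6.3.2.4 describes pre-infusion, 2-hour and 4-hour ECGs as the minimum at all treatment visits after Cycle 1, and SAP Table 2 marks the 4-hour row at every one of them.

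**The concern.** QT prolongation is the drug's main identified risk, and the protocol justifies the risk by saying patients are watched until it has passed. A discharge rule that can end observation before the protocol's own later mean peak does not match that justification.

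It also affects the data. The dose-reduction rule, the reporting of QTc prolongation as an adverse event of special interest, and the any-time QTcF categories in SAP Section 14.4 all depend on what the ECGs record. A first rise that comes after the 2-hour reading would be neither recorded nor acted on.

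The SAP's different account of the 4-hour ECG means a reader of the report could believe that later infusions were covered to 4 hours when the protocol did not require it.

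**Working it through.** **1. The protocol's lag figure.** Section 2.3.2 gives a lag of up to 2 to 3 hours after peak concentration, which it places at the end of infusion. The two study peaks, 2 hours (TH-CR-602) and 3 hours (TH-CR-601), reproduce that range.

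**2. One time scale.** Hours after the end of infusion = hours after the start − infusion length. Section 6.2.2 sets at least 1 hour; I use 1 hour.

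| Source | Hours after end of infusion | Gap after a 2-hour discharge |
|---|---|---|
| Table 7, after Cycle 2 Day 1 | 2 | – |
| TH-CR-602 mean maximum (Section 2.3.2) | 2 | 2 − 2 = 0 h |
| TH-CR-601 mean maximum (Section 2.3.2) | 3 | 3 − 2 = 1 h |
| Lag to peak QTc (Section 2.5) | about 3 | about 1 h |
| 3 to 4 h from start of infusion (Section 2.5) | 3 − 1 = 2 to 4 − 1 = 3 | 0 to 1 h |
| Latest observed prolongation (Section 2.6) | up to 4 | up to 4 − 2 = 2 h |

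Section 6.9.2 allows ±10 minutes, so the nominal 2-hour ECG may be taken at 1 h 50 min, before both mean peaks.

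**3. Who is exposed to the gap.** Under Table 7 and Section 6.9.2.1, QTcF of 501 msec or more, or a rise above 60 msec, brings ECGs every 15 to 30 minutes, and discharge waits for two acceptable readings after the 4-hour point. Such an event at the previous infusion brings hourly ECGs for 4 hours. A patient released at 2 hours therefore has QTcF of 500 msec or less and a rise of 60 msec or less, with no Grade 3 event at the previous infusion. What can be missed is a first late peak in these patients.

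**4. How many infusions.** ECGs to 4 hours for everyone: 4 (Cycle 1) + 1 (Cycle 2 Day 1) = 5. Section 11.3 expects up to 10 cycles.
- 10 cycles: 10 × 4 = 40; 40 − 5 = 35; 35/40 = 87.5%.
- 2 cycles: 2 × 4 = 8; 8 − 5 = 3; 3/8 = 37.5%.

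These are upper counts, because patients meeting the conditions in step 3 leave the 2-hour rule for the infusions concerned.

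**5. What cannot be computed.** For TH-CR-601 the protocol gives the mean change at its maximum but not at 2 hours, and it gives no time course for later cycles. The number of missed Grade 3 events cannot be derived.

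**The case against.** **The step-down may be deliberate.** Patients reach the 2-hour rule only after five infusions with ECGs to 4 hours, and release requires Grade 2 or lower and no symptoms. That is a reasonable design idea, but the protocol does not state it. Section 2.3.2 reports no accumulation by Cycle 2, and nothing in the documents shows an earlier or smaller peak in later cycles.

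**Section 2.5 also counts from the start of infusion.** On that count, a 2-hour discharge after a 1-hour infusion falls at 3 hours, the lower end of its 3-to-4-hour window. This softens the conflict but leaves up to 1 hour uncovered. Sections 2.3.2 and 2.6 count from the end of infusion.

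**The larger mean maximum is at 2 hours.** This stands. A reader might infer that the 2-hour ECG misses the peak altogether; for TH-CR-602 it coincides with it. Both peaks are also group means from the first infusion.

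**A discharge at 500 msec is a narrow case.** This stands too. Since 500 − 60 = 440, a pre-infusion value below 440 msec would make the rise exceed 60 msec and trigger Grade 3 monitoring. With pre-infusion QTcF required to be below 450 msec, the case needs a value of about 440 to 449 msec or an exception agreed with the Medical Monitor.

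**The SAP may give the 4-hour ECG to everyone.** If so, the recorded data have no such gap. But that contradicts Protocol Section 6.9.2 and does not fit discharge at 2 hours. A footnote on the ECG heading of SAP Table 2 refers to patients with Grade 3 prolongation, but Section 6.3.2.4 carries no such limit. The documents do not settle which coverage was obtained.

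**Conclusion.** The inconsistency holds. After Cycle 2 Day 1, an asymptomatic patient with QTcF of Grade 2 or lower may leave up to 1 hour before the later of the two mean peaks and 2 hours before the end of the observed window, despite the promise of supervision throughout the at-risk period. This applies to at most 35 of 40 infusions over 10 cycles and 3 of 8 over two. It assumes nominal ECG times, a Cycle 1 Day 1 time course that carries over to later cycles and, for the start-based window only, a 1-hour infusion.

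Two stronger readings are not supported. A reader might infer that late-cycle Grade 3 incidence is understated; it could be, but no later-cycle time course is given. A reader might also take the 10 patients (21%) with QTcF of 501 msec or more in the earlier studies as the size of the harm. That figure counts everyone who reached the level, not those who first reached it after 2 hours, and it does not describe patients already followed to 4 hours through five infusions.

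The SAP conflict is separate and firm: its Section 6.3.2.4 and Protocol Section 6.9.2 cannot both describe the ECGs after Cycle 2 Day 1.

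**What to change.** Reconcile Table 7, Section 6.9.2, the Schedule of Events, and SAP Section 6.3.2.4 and Table 2 with the risk-period statements in Sections 2.3.2, 2.5 and 2.6. This review does not propose a discharge time or an ECG schedule.

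The study was discontinued with 41 patients enrolled and the database is locked, so the practical change is in the report:
- Split the any-time QTcF categories in SAP Section 14.4 by the coverage actually obtained at each infusion: ECGs to 4 hours, or 2 hours only.
- State that infusions with only a 2-hour ECG do not cover the full documented period of prolongation, which runs up to 4 hours.
- Do not read the difference between the two groups as an estimate of missed events. Under Section 6.9.2, a 4-hour ECG in later cycles may have been taken because prolongation had already been seen.

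The cost is one extra split of a table already planned, from ECG times already held, plus wording to align the documents.

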6.7.2 Treatment Guidelines for Infusion-related Reactions

Treatment and management of infusion-related reactions will be based on the severity and type of symptom(s) experienced. Treatment guidelines for infusion-related reactions are presented in Table 8.

Table 8: Treatment Guidelines for Infusion-Related Reactions

Grade (CTCAE v5.0)	Definition	Treatment Guideline
Grade 1	 Mild transient reaction Infusion interruption not indicated Intervention not indicated 	 Monitor for at least 2 hours after the end of the infusion Provide patient instructions and prophylactic medications at discharge as appropriate Consider adjusting premedication based on symptoms for subsequent infusions
Grade 2	 Therapy or infusion interruption indicated but responds promptly to symptomatic treatment Prophylactic medications indicated for ≤ 24 hours 	 Administration of medications (e.g., anti-histamines, steroids, NSAIDs and IV fluids), as appropriate Monitor for at least 2 hours after the end of the infusion Consider adjusting premedication based on symptoms for subsequent infusions
Grade 3	 Prolonged (e.g., not rapidly responsive to symptomatic medication and/or brief interruption of infusion) Recurrence of symptoms following initial improvement, hospitalization indicated for clinical sequelae 	 Administration of medications (e.g., anti-histamines, steroids, NSAIDs and IV fluids), as appropriate Hospitalization for medical care and observation Reduce tarloxotinib dose to 120 mg/m² for subsequent doses*, or consider slowing infusion rate, and/or adjusted premedication after discussion with the Medical Monitor If Grade 3 infusion reaction recurs after this initial dose reduction, then reduce the tarloxotinib dose to 75 mg/m² for subsequent doses*
Grade 4	Life-threatening consequences Urgent intervention indicated	Hospitalization for urgent medical treatment Discontinue tarloxotinib permanently

CTCAE = Common Terminology Criteria for Adverse Events; IV = intravenous; NSAID = nonsteroidal anti-inflammatory drug

^{*} Dose re-escalation may be permitted following discussion and approval by the Medical Monitor

Confidential and Proprietary

6.7.3 Treatment Guidelines for Other Non-Hematologic Toxicity

Table 9 provides treatment guidelines for treating tarloxotinib non-hematologic toxicities other than QT prolongation and infusion-related reactions.

Table 9: Treatment Guidelines for Tarloxotinib-Related Non-Hematologic Toxicity

Toxicity (CTCAE v5.0)	Details	Hold Dose	Dose Levels After Recovery to ≤ Grade 2 or Baseline
Grade 2 Intolerable	Intolerable skin toxicity or diarrhea	Hold dose until resolution to Grade 0 or 1 or Grade 2 tolerable	If symptoms are intolerable, recurrent, or not controlled by supportive care, hold dose until symptoms improve and reduce to next lower dose level
Grade 2	ALT or AST > 3 x ULN	Hold dose until resolution to < Grade 2 or baseline	150 mg/m ² (no reduction)
	ALT or AST > 3 x ULN (Grade 2) AND a total bilirubin \geq 2 x ULN (patients without liver metastasis)**	Treatment to be discontinued	Not applicable
Grade 3	Except nausea and vomiting*	Hold dose until resolution to Grade 0 or 1 or Grade 2 tolerable	120 mg/m ² ; if recurs, then second reduction to 75 mg/m ²
Grade 4	Life-threatening conditions	Treatment to be discontinued	Not applicable
Grade 4	Except fatigue and non-life-threatening pulmonary embolism that are adequately treated	Hold dose until resolution to Grade 0 or 1	120 mg/m²; if recurs, then second reduction to 75 mg/m²

ALT = alanine aminotransferase; ASP = aspartate aminotransferase; CTCAE = Common Terminology Criteria for Adverse Events; ULN = upper limit of normal

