6.5 Treatment and Retreatment Criteria

The result of tumor assessments is not required for the initiation of subsequent cycles, but patients must meet the following criteria before receiving each tarloxotinib infusion. **Note:** all ECG dose modifications will be based on the average manually measured QTcF.

• No QTcF of \geq 601 msec during any previous infusion

Note: Patients with QTcF of ≥ 501 msec and < 601 msec during or following the prior infusion MUST be dose reduced. If QTcF prolongation is \geq Grade 3, an ECG may need to be repeated more frequently during a patient's visit as indicated in Table 7, depending on the degree of the prolongation and per institutional standards.

- Check serum electrolytes
 - Pre-infusion magnesium and calcium in normal range, unless an exception is approved by the Medical Monitor.
 - o If other electrolytes (eg, sodium, chloride) are outside of the normal range, patient can receive tarloxotinib infusion if it is deemed safe per Investigator discretion.
 - o Pre-infusion serum potassium must be ≥ 3.5 mEq/L.
- Pre-infusion ECG

Confidential and Proprietary

- o No evidence of second- or third-degree atrioventricular block
- o QTcF interval of < 450 msec
- Skin rash of \leq Grade 2
- Gastrointestinal toxicity of \leq Grade 2
- Any other clinically significant tarloxotinib-related toxicity must return to at least Grade 2.

All patients not meeting retreatment criteria must be discussed with the Medical Monitor (or designee) and possible dose/schedule modification and/or study treatment discontinuation discussed.

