AEs must be reported using standard medical terminology. The use of abbreviations (standard and nonstandard) should be avoided to help ensure a clear understanding of the event. An example of a standard abbreviation that may have several meanings is "MI" which could mean "myocardial infarction" or "mitral insufficiency." All AE terms will be coded using a standardized dictionary (i.e., Medical Dictionary for Regulatory Activities [MedDRA®]). Generally, when reporting a well-known and understood condition, it is preferable to report the overall diagnosis rather that the individual signs and symptoms; the exception to this rule in this study is when the patient experiences an infusion reaction (i.e., infusion-related reaction). The term "intermittent" should be avoided as the duration and incidence of events helps in understanding the safety profile of the study drug.

8.2.2 **Adverse Event Severity**

AEs will be reported at the highest experienced. AE severity will be graded according to NCI CTCAE v5.0. A copy of the document will be provided to investigational sites and an electronic version is available at:

https://ctep.cancer.gov/protocolDevelopment/electronic applications/docs/CTCAE v5 Quick R eference 8.5x11.pdf

Events not listed in NCI CTCAE will be graded according to the criteria described in Table 10.

Confidential and Proprietary

Table 10: Severity Grading Guideline for Adverse Events Not Listed in NCI CTCAE

Adverse Events Not Listed in NCI CTCAE v5.0			
Grade	Description		
1	Mild; Asymptomatic or mild symptoms; Clinical or diagnostic observations only; Intervention not indicated		
2	Moderate; Minimal, local or noninvasive intervention indicated; Limiting age-appropriate instrumental activities of daily living*		
3	Severe or medically significant but not immediately life-threatening; Hospitalization or prolongation of hospitalization indicated; Disabling; Limiting self-care activities of daily living**		
4	Life-threatening consequences; Urgent intervention indicated		
5	Death related to adverse event		

Adapted from NCI CTCAE v5.0

NCI CTCAE = National Cancer Institute Common Terminology Criteria for Adverse Events

Note: A semicolon indicates "or" within the description of the grade.

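### Table 9 does not give one instruction for every Grade 4 toxicity, and in two rows its hold cell sets a stricter recovery level than its dose-column heading

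*Protocol*

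**What the plan says.** Protocol Section 6.7.3, Table 9, sets the action for tarloxotinib-related toxicity other than QT prolongation and infusion reactions. Section 6.7 also sends related Grade 3 or 4 neutropenia and thrombocytopenia to it.

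- First Grade 4 row: scope "Life-threatening conditions", action "Treatment to be discontinued", no later dose.
- Second Grade 4 row: scope "Except fatigue and non-life-threatening pulmonary embolism that are adequately treated", action "Hold dose until resolution to Grade 0 or 1", then 120 mg/m², and 75 mg/m² on recurrence.
- Grade 2 ALT/AST row: "Hold dose until resolution to < Grade 2 or baseline", then the full 150 mg/m².
- Heading of the dose column, over all rows: "Dose Levels After Recovery to ≤ Grade 2 or Baseline".

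Section 6.5 lists conditions to be met before each infusion. Rash and gastrointestinal toxicity may be Grade 2 or lower. For the rest: "Any other clinically significant tarloxotinib-related toxicity must return to at least Grade 2". I read this as Grade 2 or lower. Neither section says which prevails when they differ.

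**The concern.** The table decides whether a patient with the most severe toxicity comes off the drug for good or is re-dosed. If one event fits two rows with different actions, or fits none, sites must improvise. Likewise, if the level that ends a hold differs from the level at which the next dose is defined, two sites can treat the same patient differently and each can point to the protocol.

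The statistical stake is in the safety output. SAP Section 14.1 tabulates adverse events leading to discontinuation, and Section 12.1 summarises cycles and dose intensity. Inconsistent stop-or-resume decisions would feed into these. They would not show up as deviations either: protocol Section 6.8 makes dose modification a compliance item, but SAP Section 11.2 neither lists nor summarises deviations.

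**Working it through.** No stated figure is involved, so the check sets the passages side by side.

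**Step 1. How can the word *Except* be read?** The Grade 3 row of the same table uses it to remove nausea and vomiting from that row, and a footnote gives their handling. Reading A applies that usage: the second Grade 4 row covers all Grade 4 events other than the two named. Reading B treats the second row as an exception to the first: it covers only the two named events.

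| Grade 4 event | Reading A | Reading B |
|---|---|---|
| Life-threatening, neither fatigue nor embolism | Both rows: stop, and hold then resume | First row: stop |
| Numeric, not judged life-threatening | Second row: hold then resume | No row |
| Adequately treated, non-life-threatening pulmonary embolism | No row | Second row |
| Fatigue | First row if judged life-threatening, otherwise no row | Second row |

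Reading A produces an overlap and a gap; Reading B produces a gap. Unlike nausea and vomiting, the two named events have no footnote.

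**Step 2. Do numeric Grade 4 events exist?** Yes. SAP Appendix B, reproducing CTCAE v5.0, has Grade 4 for ALT above 20 × ULN (normal baseline), neutrophils below 500/mm³ and platelets below 25 × 10⁹/L, with no reference to threat to life.

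**Step 3. What separates the actions?** Permanent stop means 0 mg/m². Resumption is at 120/150 = 80% of the starting dose, then 75/150 = 50%.

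**Step 4. Hold cell against dose-column heading.** Four rows prescribe a hold.

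| Row | Hold until | Heading | Agree? |
|---|---|---|---|
| Intolerable Grade 2 skin toxicity or diarrhea | Grade 0, 1 or tolerable 2 | Grade ≤ 2 or baseline | Broadly |
| Grade 2 ALT/AST | Below Grade 2, or baseline | Grade ≤ 2 or baseline | No |
| Grade 3 | Grade 0, 1 or tolerable 2 | Grade ≤ 2 or baseline | Broadly |
| Second Grade 4 row | Grade 0 or 1 | Grade ≤ 2 or baseline | No |

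The conflict is in 2 of the 4 rows. In both, the hold cell is the stricter text.

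**Step 5. A worked case.** Take a patient with normal baseline ALT and a related value above 3.0 and up to 5.0 × ULN (Grade 2, SAP Appendix B). The dose-column heading is satisfied and so is Section 6.5; the hold cell is not. Section 6.5 requires Medical Monitor discussion only for patients who fail its criteria, and this patient passes. Section 6.2.3 requires discussion of schedule changes of more than 1 day, so a site that holds beyond a day reaches the Medical Monitor, while a site that doses on schedule need not.

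**The case against.** The strongest reply is that a sensible reader can make the table work. The first Grade 4 row is confined to life-threatening conditions, and under Reading B the two rows do not collide. Section 6.5 states minimum conditions, so a stricter toxicity-specific hold can be obeyed alongside it and the patient in Step 5 is simply held. The Medical Monitor is involved in most departures from schedule.

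Much of this stands. Reading B removes the overlap, though not the gap. The cumulative view of Section 6.5 is reasonable, but it is not written down and does not explain why the table's own heading differs from its hold cells.

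A reader might also infer more than the documents support:

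- *That the two rows flatly contradict each other for every Grade 4 event.* Table 10's Grade 4 wording, "Life-threatening consequences; Urgent intervention indicated", might suggest that Grade 4 is always life-threatening. But Table 10 covers only events not listed in CTCAE, and some CTCAE Grade 4 limits are purely numeric.
- *That the recovery heading contradicts Section 6.5.* It does not; both accept Grade 2. The two hold cells are what differ.
- *That the Grade 3 row conflicts too.* Its hold level fits within the heading.
- *That every ALT/AST value above 3 and up to 5 × ULN fails the hold.* The hold cell also accepts a return to baseline, and Section 5.1 admits patients with liver metastases at up to 5 × ULN.
- *That a prolonged hold ends treatment automatically after two missed doses.* Section 5.3 lets such patients continue with Medical Monitor agreement, and the toxicity-delay rule in Section 6.7 (more than 3 weeks) also has a Medical Monitor exception.

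**Conclusion.** The point holds in a limited form. Neither available reading of Table 9 gives one instruction for every Grade 4 toxicity, and the text does not say which reading applies. In two of the four hold rows the hold cell is stricter than the dose-column heading, and also stricter than Section 6.5, with no rule on how they combine.

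How many patients are affected cannot be estimated. Study TH-CR-601 reported one related Grade 4 event in 21 patients (1/21 = 4.8%), a cerebrovascular accident. That shows related Grade 4 events occur; it does not show that one was handled inconsistently. Section 6.7 reports no hematologic toxicity associated with the drug to date, so that route is so far hypothetical.

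No efficacy calculation rests on this. The study closed early with 41 patients enrolled, so the practical consequence is for reading toxicity discontinuations and dose reductions, and for any reuse of the table. Nothing here implies a view on which clinical rule is right. The conclusion assumes that the Section 6.5 line means Grade 2 or lower.

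**What to change.** Reconcile the passages; the sponsor's clinical team chooses the rules.

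1. Reword the two Grade 4 rows so that each Grade 4 event falls in exactly one. State where fatigue and adequately treated, non-life-threatening pulmonary embolism go, and where numeric events not judged life-threatening go, including neutropenia and thrombocytopenia.
2. In the Grade 2 ALT/AST row and the second Grade 4 row, make the hold cell and the dose-column heading state the same recovery level.
3. Add one line to Section 6.5 saying how its criteria and Table 9's hold levels apply together.

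The cost is wording in one table and one line of Section 6.5, with no new assessments. Because enrolment has ended, the study report could also state how Grade 4 events and the two affected hold rules were handled in practice.
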